6.4. Concomitant Medications and Prohibit Medications

6.4.1.Concomitant Medications

Concomitant medications include any prescription or over-the-counter (OTC) medications used from the screening period (within 28 days prior to the first dose) to the safe follow-up period. All concomitant medications will be recorded in detail. The following drugs are allowed during the study:

- Subjects with other diseases may continue to receive the relevant medications as required or at any time during the study period;
- Symptomatic treatment for AEs;
- Best supportive care. Subjects with bone metastases can receive bisphosphonate treatment.

Subjects can also undergo palliative radiotherapy for bone metastasis cancerous pain.

6.4.2. Prohibit Medications

Prohibit concomitant use with Chinese herbal medicine during the single-dose PK study period and the first treatment cycle to avoid interfering with the 3D185 PK study.

Prohibit concomitant use with gastric acid reducing agents throughout the treatment period.

Prohibit concomitant use with other specific anti-tumor drugs, including chemotherapy, targeted therapy, immunotherapy, and Chinese herbal medicine with anti-tumor indication throughout the study.

Prohibit concomitant use with P-glycoprotein (P-gp) inhibitors throughout the treatment period.

Prohibit concomitant use with CYP3A4 strong inducers or CYP3A4/CYP2C8 strong inhibitors and strong dual inhibitors. (see Appendix 6 for details).

CYP3A4 moderate inhibitors (amprenavir, aprepitant, atazanavir, ciprofloxacin, darunavir, ritonavir, diltiazem, erythromycin, fluconazole, fosamprenavir, imatinib, and verapamil) and CYP3A4/2C8 moderate dual inhibitors (trimethoprim, ticagrelor, nifedipine) are not recommended throughout the treatment period.

Prohibit long-term use of high-dose anticoagulant or antiplatelet agents throughout the treatment period (e.g., warfarin >2 mg/day, aspirin \geq 300 mg/day, clopidogrel \geq 75 mg/day).

If the subject needs palliative radiotherapy (e.g., local radiation therapy to relieve cancerous pain for subjects with bone metastases) for symptom relief during treatment period, the investigational

product should be discontinued during radiation therapy. Subjects can resume the investigational product 7 days after the completion of radiation therapy and must meet the following conditions:

- Radiation-related toxicity has recovered to Grade ≤ 2 ;
- No disease progression occurs.

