5.3. Exclusion Criteria

Subjects who meet any of the following criteria should be excluded from the study:

- 1. Subjects who received other investigational products or devices in other clinical trials within 4 weeks before the first dose.
- 2. Subjects who received anti-tumor therapy (except for mitomycin, nitrosourea, and fluorouracil oral drugs) within 4 weeks before the first dose, including but not limited to chemotherapy, radiotherapy (palliative radiotherapy is completed at least 2 weeks before the first dose can enroll), targeted therapy or immunotherapy.

Note: The last dose of mitomycin and nitrosourea should be at least 6 weeks before investigational product initiation; the last dose of oral fluorouracil such as tegafur and capecitabine should be at least 2 weeks before investigational product initiation.

- 3. Subjects who previously received selective FGFR1-3 inhibitor therapy.
- 4. Subjects who require the use of concomitant medications that prolong the QT/QTc interval.
- 5. Subjects who have previous toxicity of anti-tumor therapy that has not recovered to Grade 0 or 1. (alopecia, chemotherapy-induced peripheral neurotoxicity, and ototoxicity \leq Grade 2 can enroll).
- 6. Subjects who received CYP3A4 and/or CYP2C8 strong inhibitors or CYP3A4 strong inducers (see Appendix 6) within 14 days prior to the first dose and the subjects who need to continue using these drugs.
- Subjects who have any of the following eye diseases/conditions: 1) History of RPED;
 History of laser treatment or intraocular injection for macular degeneration; 3) History of dry or wet age-related macular degeneration; 4) History of RVO; 5) History of retinal degenerative diseases; 6) History of chorioretinal lesions.
- 8. Subjects who received clinical intervention for biliary obstruction 14 days prior to the first dose or the Investigator judges that the symptoms have not resolved or require anti-infective treatment.
- 9. Subjects who have gastrointestinal disorders that will affect oral administration or the Investigator judges that the absorption of 3D185 will be interfered.

- 10. Subjects underwent major surgery (except biopsy) within 4 weeks, or the surgical incision has not completely healed prior to the first dose.
- 11. Subjects who had clinically uncontrollable pleural effusion, ascites, or pericardial effusion within 2 weeks prior to the first dose.

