APPENDIX 6 CYP3A4 STRONG INHIBITORS AND INDUCERS, AND CYP2C8 STRONG INHIBITORS

Table 11 CYP3A4 Strong Inhibitors and Inducers, and CYP2C8 Strong Inhibitors

CYP3A4 Strong Inhibitors	Nelfinavir, Indinavir, Voriconazol, Telithromycin, Ketoconazole, Nefazodone, Itraconazole, Clarithromycin, Saquinavir, Darunavir, Posaconazole, Lopinavir, Telaprevir, Boceprevir, Idelalisib, Cobicistat, Stiripentol, Curcumin, Ritonavir, Conivaptan, Troleandomycin, Mibefradil, Doxycycline, Efavirenz, Atazanavir, Tipranavir, Naloxone, Clotrimazole, Nilotinib, Laveridine, Loperamide, Ribociclib, Danoprevir, Elvitegravir, Midostaurin, Terfenadine, Ergotamine, Econazole
CYP3A4 Strong Inducers	Nevirapine, Rifampicin, Carbamazepine, Fosphenytoin, Pentobarbital, Phenobarbital, Phenytoin, Primidone, Rifapentine, Enzalutamide, Lumacaftor, St. John's Wort, Mitotane, Apalutamide, Quinine, Rimexolone, Rifaximin, Rifamycin, Topiramate, Oxcarbazepine, Midostaurin
CYP2C8 Strong Inhibitors	Gemfibrozil, Clopidogrel, Lopinavir, Fluvoxamine, Felodipine, Mometasone furoate, Zafirlukast, Sorafenib, Erlotinib, Dabrafenib, Troglitazone, Candesartan cilexetil, Salmeterol, Cholecalciferol, Trametinib, Fluticasone, Fluticasone furoate, Fluticasone propionate, Ritonavir

https://www.drugbank.ca/categories

Subject's other concomitant medications can be judged by reference to their instructions.

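### Section 6.4 and Appendix 6 give conflicting rules for atazanavir, darunavir, ritonavir and clopidogrel, and the necessity clause in 6.4.3 has no strength limit

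*Protocol*

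**What the plan says.** Section 6.4.2 sets a ban, "Prohibit concomitant use with CYP3A4 strong inducers or CYP3A4/CYP2C8 strong inhibitors and strong dual inhibitors", and refers to Appendix 6 for the names. The following paragraph sets a weaker tier. It begins "CYP3A4 moderate inhibitors (amprenavir, aprepitant, atazanavir, ciprofloxacin, darunavir, ritonavir" and runs to 12 moderate CYP3A4 inhibitors, followed by three moderate dual CYP3A4/2C8 inhibitors. All 15 are advised against during treatment, not forbidden.

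The same section bars long-term, high-dose antiplatelet use and gives clopidogrel from 75 mg/day as an example. Exclusion 17 in 5.3 uses the same threshold.

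Section 6.4.3 says that CYP3A4 inhibitors and inducers, with no distinction by strength, should be prohibited. It then leaves room for their use where the investigator thinks it necessary, with close monitoring for lost efficacy or added toxicity.

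At entry, exclusion 6 removes "Subjects who received CYP3A4 and/or CYP2C8 strong inhibitors or CYP3A4 strong inducers (see Appendix 6) within 14 days prior to the first dose", and also subjects who need to go on taking such drugs.

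**The concern.** The protocol (2.2.1.1) names CYP3A4 as the main CYP enzyme metabolizing 3D185, so these rules protect the exposure on which DLTs and PK are read. As written, one section both bans and merely discourages the same three drugs, and the next section can be read as reopening the ban for strong CYP3A4 agents in general. Two sites could answer differently when asked whether such a drug may be started during the DLT evaluation period.

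Decisions in this trial rest on few subjects. In accelerated titration, one drug-related Grade 2 or higher event in a single subject converts the design to i3+3. In a cohort of three, one DLT changes the recommendation. The protocol already treats the early period as worth protecting: 6.4.2 bans Chinese herbal medicine "during the single-dose PK study period and the first treatment cycle to avoid interfering with the 3D185 PK study".

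**Working it through.** The protocol states no figure to reproduce on this point. The check compares the lists and then the rules.

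**1. Overlap of the lists.** Inputs: the two moderate lists in 6.4.2 (12 and 3 names) and Appendix 6, Table 11 (38 strong CYP3A4 inhibitors, 19 strong CYP2C8 inhibitors, and the strong CYP3A4 inducers).

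- Darunavir is in the strong CYP3A4 list: "Clarithromycin, Saquinavir, Darunavir, Posaconazole".
- Ritonavir is there too: "Stiripentol, Curcumin, Ritonavir, Conivaptan". It also closes the strong CYP2C8 list.
- Atazanavir is there too: "Mibefradil, Doxycycline, Efavirenz, Atazanavir, Tipranavir".
- No other name in the moderate list appears in Appendix 6. The overlap is 3/12 = 25% of the moderate CYP3A4 inhibitors, or 3/15 = 20% of all drugs advised against.
- None of the three moderate dual inhibitors (0/3) is in Appendix 6.

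Lopinavir is also in both strong-inhibitor lists, but it is not in the moderate list, so it raises no conflict.

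**2. Clopidogrel.** Appendix 6 lists it as a strong CYP2C8 inhibitor. Through that list, 6.4.2 bans it on treatment and exclusion 6 bars it in the 14 days before the first dose, in both cases at any dose. The antiplatelet sentence in 6.4.2 and exclusion 17 bar it only from 75 mg/day. Below that dose the protocol gives two answers.

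**3. Section 6.4.3 against 6.4.2.**

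| Agent | 6.4.2 | 6.4.3 |
|---|---|---|
| Strong CYP3A4 inhibitor or inducer | Banned | Should be prohibited; usable if judged necessary |
| Moderate CYP3A4 inhibitor | Advised against | Should be prohibited; usable if judged necessary |
| Atazanavir, darunavir, ritonavir | Banned through Appendix 6 and advised against by name | Should be prohibited; usable if judged necessary |

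For strong agents the necessity clause is looser than 6.4.2. For moderate agents the general rule in 6.4.3 is stricter than 6.4.2. Neither section says which prevails. The clause concerns CYP3A4 only, so it does not resolve the clopidogrel conflict.

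**4. Whether the entry criteria close the gap.** Exclusion 6 covers use in the 14 days before the first dose and a continuing need at entry. It does not cover a drug first needed after dosing starts.

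**5. The data exposed.** The DLT evaluation period is 7 + 28 = 35 days and contains both the single-dose and the Cycle 1 PK sampling. Under the Appendix 7 rule with an equivalence interval of 16% to 30%:

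- 0/3 = 0%, below 16%: escalate.
- 1/3 = 33%, above 30%, and (1 − 1)/3 = 0% is below 16%: stay.
- 2/3 = 67%, above 30%, and (2 − 1)/3 = 33% is not below 16%: de-escalate.

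This shows how much one subject can weigh. It does not show that a co-medication will produce a DLT.

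**6. Supportive care.** Appendix 6 also lists loperamide ("Nilotinib, Laveridine, Loperamide, Ribociclib") and doxycycline (in the atazanavir run quoted above) as strong CYP3A4 inhibitors. Section 6.4.1 allows symptomatic treatment of adverse events. Under 4.5, diarrhea of Grade 3 or higher escapes DLT status only if symptomatic treatment controls it within 48 hours. Whether loperamide may be used therefore bears on DLT classification. At present only a literal reading of 6.4.3 would clearly allow it.

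**The case against.** The best defence is that advising against a drug authorises nothing: a site that simply avoids the three drugs satisfies both sentences of 6.4.2. Likewise, 6.4.3 is most coherently read as a general rationale whose necessity clause applies to agents that 6.4.2 does not already ban. A medical-necessity clause with monitoring is a legitimate choice, and co-medication is recorded (6.4.1), weighed in causality (8.5.2) and open to SMC review (4.1). Exclusion 6 also removes anyone with an ongoing need at entry, so only new starts on study remain.

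Much of this stands, and it limits the weight of the point. It does not remove the conflict. Naming a drug as moderate tells a site that the ban on strong agents does not apply to it, and the narrower reading of 6.4.3 is not written down. Recording, causality assessment and SMC review come after the exposure.

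It can also be said that Appendix 6 is not self-evidently the right list, since it puts midostaurin among both the strong inhibitors and the strong inducers. That is fair. The case for following it is that both exclusion 6 and the ban in 6.4.2 refer to it.

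A reader might infer that DLT or PK data will be distorted and the MTD misjudged. The documents do not support that: they give neither the size of any exposure change nor the number of subjects likely to need such a drug. A reader might also want non-strong agents avoided during the DLT evaluation period. That is a preference; the protocol commits no error by leaving it to monitored judgement.

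**Conclusion.** The inconsistency is real and should be corrected. Three drugs are both banned and merely discouraged, clopidogrel below 75 mg/day is both banned and not barred, and 6.4.3 read literally permits strong CYP3A4 agents that 6.4.2 forbids. The size is a matter of list membership (3 of 12 names, plus clopidogrel), not of measured risk, and the practical gap is a drug started on study. It would go too far to say that the protocol knowingly permits these drugs or that 6.4.3 overrides 6.4.2; the protocol does not say which section prevails. The conclusion rests on Table 11 as printed and on Appendix 6 being the operative list of strong agents, as 6.4.2 and exclusion 6 both make it.

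**What to change.** - In 6.4.2, delete atazanavir, darunavir and ritonavir from the moderate list, leaving 12 − 3 = 9 moderate CYP3A4 inhibitors and the three dual inhibitors, so that the Appendix 6 ban applies.
- State one rule for clopidogrel and use it in 6.4.2, exclusions 6 and 17, and Appendix 6.
- In 6.4.3, state that the exception is subject to 6.4.2 and covers only CYP3A4 inhibitors and inducers that are not strong, with the existing monitoring.
- In the same edit, say whether loperamide and doxycycline are allowed as named supportive-care exceptions. This should not be left open, because closing 6.4.3 to strong agents without deciding it would remove loperamide by default.

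The cost is a short text amendment with no new data collection. The small downside is that investigators lose discretion to start a strong CYP3A4 agent while the subject stays on 3D185.

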6.4.3. Drug-Drug Interactions

Preclinical data showed that 3D185 is primarily catalyzed by CYP3A4. Besides, CYP2C8, CYP2D6, and CYP3A5 also participated a little bit. Therefore, the concomitant use of CYP3A4 inducers and inhibitors should be prohibited in clinical trials. If the Investigator considers it is necessary to concomitant use, it needs to closely monitor the possible reduced efficacy or increased toxicity due to the concomitant use.

6.5. Treatment compliance

The Investigator should accurately record the date and amount of each subject's actual study medication. Subjects will be required to return all kits, bottles, unused tablets, etc. at every visit. The treatment compliance should be estimated during the study and be recorded in the appropriate sections of the eCRF. The Investigator should calculate the actual dose by counting the number of unused tablets returned per cycle, and the Investigator will also need to collect data from the subject diary. In the diary, subjects should record the number of all tablets taken and the corresponding number of times.

Any non-compliance for any reason should be recorded. Subjects who postpone treatment for more than 14 days for reasons other than medical care will be defined as poor compliance. If there is a poor compliance, the Investigator will decide whether to discontinue the study treatment based on the subject's condition.

7. EVALUATION INDICATORS AND EVALUATION CRITERIA

7.1. Screening Period

All subjects must sign ICF prior to the start of the study-related examination or operation. The study center should maintain the ICFs signed by the subjects, including those not enrolled.

During the screening period, complete prior medical history, demographic information, tumor history and prior tumor treatment history, vital signs, physical examination, and ECOG performance status should be recorded. The screening exams and evaluations should be performed within 28 days prior to the first dose. To avoid repeat exam, the results of clinical routine examination (such as echocardiography, virologic examination, tumor imaging evaluation) before informed consent are acceptable if within 28 days prior to the first dose. CBC with differential, serum chemistry, coagulation parameters, urinalysis, serum β -hCG test, 12-lead ECG, and ophthalmological examination should be performed within 7 days prior to the start of study treatment. The detailed screening examinations and evaluations can refer to Table 4 study flow chat.

Any prior medications taken within 28 days before the first dose must be recorded in the eCRF. The information includes generic name, administration and dosage, the reason for the treatment, dates of start and stop, whether to continue taking the medication during this trial, etc.

After the signing of the ICF and before starting dose, any SAEs associated with the protocol required procedures should be reported.

Baseline tumor assessment should be completed by imaging (CT, MRI) according to RECIST 1.1 within 28 days prior to enrollment.

The following screening procedures will be performed within 28 days (-28 to -1 days) before the first dose:

- Informed consent;
- Demographic information (including body weight and height)
- Medical history information,
- Tumor history and prior tumor treatment history;
- Inclusion/Exclusion criteria;
- Complete physical examination (perform within 7 days before the first dose);
- ECOG performance status (perform within 7 days before the first dose);

- Vital signs (perform within 7 days before the first dose);
- CBC with differential (perform within 7 days before the first dose);
- Serum chemistry (perform within 7 days before the first dose);
- Coagulation parameters (perform within 7 days before the first dose);
- Urinalysis (perform within 7 days before the first dose);
- 12-lead ECG (perform within 7 days before the first dose);
- Ophthalmological examination (perform within 7 days before the first dose);
- Pregnancy test: serum β-hCG (female subjects at childbearing age should perform within 7 days before the first dose);
- Echocardiography (perform within 28 days before the first dose);
- Virologic examination (perform within 28 days before the first dose);
- Tumor assessment (CT or MRI, perform within 28 days before the first dose), the imaging method can be decided by the Investigator, but should be consistent before and after treatment;
- Concomitant medication;
- AE collection.

7.2. Eligible Subject Enrollment

Informed consent must be obtained before all the specific study procedures in this clinical trial. The eligibility will be determined after reviewing the inclusion/exclusion criteria. Candidates could be re-screened once if they did not fulfill the entry eligibility (failed screening) at the first screening visit. Subjects need to re-sign the ICF and obtain a new screening number during re-screening.

If an enrolled subject is found to unsatisfied the eligibility criteria, the Investigator will discuss with the Sponsor to determine whether the subject continues to participate in the study to treat with the investigational product.

7.3. Treatment Period Evaluation Indicators

7.3.1. Single Dose PK Study Period

Day 1 (C0D1)

- PK blood sample collection: within 1 h before dosing and 0.5 h (± 5 min), 1 h (± 5 min), 2 h (±5 min), 3 h (±5 min), 4 h (±5 min), 6 h (±5 min), 8 h (±5 min), and 12 h (± 5 min) after dosing;
- Record the concomitant medications;
- AE collection;
- 12-lead ECG (2 h [±5 min] after dosing).

Day 2 (C0D2)

- PK blood sample collection: 24 h (±5 min) after dosing;
- Record the concomitant medications;
- AE collection.

Day 3 (C0D3)

- PK blood sample collection: 48 h (±10 min) after dosing;
- Record the concomitant medications;
- Adverse event collection.

Day 4 (C0D4)

- PK blood sample collection: 72 h (± 10 min) after dosing;
- Record the concomitant medications;
- AE collection.

Day 5 (C0D5)

- PK blood sample collection: 96 h ($\pm 10 \text{ min}$) after dosing;
- Record the concomitant medications;
- AE collection.

7.3.2. Cycle 1 Treatment Period

C1D1 (-3/+0 days)

- Physical examination;
- Vital signs;

Confidential

- CBC with differential;
- Serum chemistry;
- Urinalysis;
- 12-lead ECG;
- Concomitant medications;
- AE collection.

C1D8 (-3/+0 days)

- Physical examination;
- Vital signs;
- CBC with differential;
- Serum chemistry;
- Urinalysis;
- 12-lead ECG;
- PK blood sample collection: within 1 h before dosing;
- Concomitant medications;
- AE collection.

C1D15 (-3/+0 days)

- Physical examination;
- Vital signs;
- CBC with differential
- Serum chemistry;
- Urinalysis;
- 12-lead ECG;
- PK blood sample collection: within 1 h before dosing;
- Concomitant medications;
- AE collection.

C1D28 (-3/+0 days)

- Physical examination;
- ECOG Performance Status;
- Vital signs;
- CBC with differential;
- Serum chemistry;
- Coagulation parameters;
- Urinalysis;
- 12-lead ECG (2 h [±5 min] after dosing);
- Ophthalmological examination;
- PK blood sample collection: within 1 h before dosing and 0.5 h (±5 min), 1 h (±5 min), 2 h (±5 min), 3 h (±5 min), 4 h (±5 min), 6 h (±5 min), 8 h (±5 min), 12 h (±5 min), and 24 (±10 min) after dosing;
- Concomitant medications;
- AE collection.

7.3.3.Cycle 2 Treatment Period

C2D15 (-3/+0 days)

- Physical examination;
- Vital signs;
- CBC with differential;
- Serum chemistry;
- Urinalysis;
- 12-lead ECG;
- Concomitant medications;
- AE collection.

C2D28 (-3/+0 days)

• Physical examination;

- ECOG Performance Status;
- Vital signs;
- CBC with differential;
- Serum chemistry;
- Urinalysis;
- 12-lead ECG;
- Tumor imaging assessment;
- Tumor tissues collection (For subjects with imaging assessments of CR, PR, or SD, it is recommended to obtain the disease-related archived tumor tissue or fresh tumor biopsy as much as possible with their consent)
- Concomitant medications;
- AE collection.

7.3.4. Cycle 3 And Additional Cycles Treatment Period

CxD28 (-3/+0 days)

- Physical examination;
- ECOG Performance Status;
- Vital signs;
- CBC with differential;
- Serum chemistry;
- Coagulation parameters (C3D28, every 8 weeks ±7 days thereafter);
- Urinalysis;
- 12-lead ECG;
- Ophthalmological examination (C3D28, every 8 weeks ±7 days thereafter);
- Echocardiography (clinically indicated);
- Tumor imaging assessment (C4D28, every 8 weeks ±7 days thereafter);

- Tumor tissues collection (For subjects with imaging assessments of CR, PR, or SD, it is recommended to obtain the disease-related archived tumor tissue or fresh tumor biopsy as much as possible with their consent.);
- Concomitant medications;
- AE collection.

7.3.5. Safety Follow-up After the Last Dose

The safety follow-up visit will be performed 28 days (± 7 days) after the last dose. Subjects who completed or prematurely discontinued investigational product therapy should return to the study center for safety assessment on 28 (± 7) days after the last dose or before starting other anti-tumor treatments, whichever occurs first. This follow-up includes assessment of AEs, laboratory tests, physical examination, ECOG scores, 12-lead ECG, ophthalmological examination, etc. Subjects who discontinued treatment for reasons other than disease progression are recommended to continue with imaging assessments at this visit.

Safety follow-up clinical evaluation indicators:

- Physical examination;
- ECOG Performance Status;
- Vital signs;
- CBC with differential;
- Serum chemistry;
- Coagulation functions;
- Urinalysis;
- 12-lead ECG;
- Ophthalmological examination;
- Echocardiography;
- Concomitant medications;
- AE collection.

